We intend to recruit up to 10 stroke survivors over the course of the study. The stroke survivors will participate in a question and answer formatted discussion with research staff to discuss the usability of the device. The clinical personnel involved in the study will participate in a voluntary feedback session to discuss the usability of the device from a clinician's perspective. We will gather feedback from the clinicians about the device. Due to the voluntary nature of the feedback gathered from clinical personnel, consent will be assumed with participation.

We plan to recruit up to 10 stroke survivors based on the following inclusion/exclusion criteria.

Inclusion Criteria

- 1. Male and female, age 18-80;
- 2. Having had a stroke (ischemic or hemorrhagic) at least 6 months prior to study enrollment:
- 3. Moderate to severe upper-limb motor impairments: score of 15-45 out of 66 on the Fugl-Meyer Scale;
- 4. Community dwelling;
- 5. Able to physically fit in the device.

Exclusion Criteria

1. Current participation in rehabilitation program targeting upper extremity function;

- 2. Cognitive impairment resulting to inability to follow instructions (MMSE ≥ 23 and subject is able to follow the 3-Stage Command) or inability to sustain attention for more than 10 minutes:
- 3. Visual impairments as assessed by the NIH Stroke Scale Visual Field subscale (only subjects with no visual loss will participate in the study);
- 4. Aphasia sufficient to limit comprehension and completion of the treatment protocol;
- 5. No more than moderate impairments in paretic UE sensation, passive range of motion, and pain that would limit ability to engage in therapy;
- 6. Increased muscle tone as indicated by score of >/= 3 on the Modified Ashworth Scale;
- 7. Previous diagnosis of neurological diseases other than stroke;
- 8. Other conditions affecting function of the stroke affected upper limb;
- 9. Individuals who present with the following:
 - open wounds
 - fragile skin
 - active infection

Briefly describe study procedures. Include any local site restrictions, for example, "Subjects enrolled at Partners will not participate in the pharmacokinetic portion of the study." Describe study endpoints.

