Data will be obtained from multiple sources: (1) Interviews of subjects, to obtain demographic information, medical history, and responses to clinical assessments. (2) Clinical examination using standard assessment tools. (3) Feedback surveys that will be filled out by study volunteers to provide the R&D team with feedback concerning the design of the BURT robotic system. (4) Data collected by sensors embedded in the robotic system.

All activities will take place at the Motion Analysis Laboratory (MAL). The study involves up to 21 visits in total within a 7 week period. The total duration may vary within this 7 week period to accommodate missed study visits.

Visit number 1:

Potential subjects who are deemed eligible during initial contact (usually by phone) will be invited to attend an in-person screening to ensure that all inclusion and exclusion criteria are met. The first session will consist of consent and screening of the subject. The procedure will start with the Mini-Mental State Examination (MMSE) for the assessment of an individual's ability to follow instructions sufficiently for the successful completion of study protocol. If the MMSE score is less than 23, the subject will be excluded from the study and the procedure will stop.

Since it is relatively common for people to have impaired decision-making capability after a stroke, prospective study volunteers' decision-making capacity and ability to give consent will be assessed using the University of California at San Diego Brief Assessment of Consent Capacity (UBACC) Questionnaire. If the subject demonstrates that he/she is able to understand the study procedures and provide consent, we will proceed to obtain informed consent. In the event that a potential subject fails the UBACC, they will be excluded from the study.

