Informed consent will be obtained by study staff members who have completed the Partners Healthcare System's human subject protection educational requirements, and the CITI Program in Protection of Human Subjects, in compliance with all Federal regulations regarding such training. Prospective subjects will be interviewed to determine preliminary eligibility. Informed consent will be obtained and subjects will be enrolled in the study prior to any clinical or laboratory testing. Subjects will be given a copy of the IRB approved consent form during the initial interview, and study staff will explain in detail the nature of the informed consent process, study purpose and procedures, time commitments, risks, potential benefits, treatment alternatives, rights as research participants, study staff contact information, confidentiality

procedures, and arrangements for medical care provided in case of injury during the study. Participants will be provided with a signed copy of the completed consent form.

• Visit number 2:

Baseline outcomes assessment battery. The clinical assessment session will last approximately $1 \frac{1}{2}$ to 2 hours. A battery of standardized measures for upper extremity in stroke rehabilitation will be administered. The battery will include: (1) range of motion and muscle strength assessment, (2) spasticity evaluation with the Modified Ashworth Scale, (3) Fugl-Meyer Assessment of upper extremity including pain and sensation subtests, (4) Wolf Motor Function Test and (5) the Motor Activity Log. All are reliable and valid measures of upper extremity motor capacity and function. We will also use the Goal Attainment Scaling to identify specific goals to focus on during the intervention. The Fugl-Meyer is our primary outcome measure and the Goal Attainment Scale our secondary outcome measure. The remaining outcome measures will be exploratory.

• Visit number 3-20:

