Intervention. Participants will receive robot-assisted upper extremity research therapy using the BURT (figure 1, page 1). The BURT provides position-controlled exercises during computerized games that emphasize repetitive movements of the paretic upper extremity. Rest periods will be offered between games, as needed. During the first treatment session, the BURT will be adjusted for the participant's arm size and the workspace will be measured via standard procedures. Subjects will be instructed to perform a series of motor tasks using the BURT system. All tasks will be performed in a seated position. Arm movements will be remapped into a virtual environment and displayed on a computer screen to enable feedback. The motor tasks to be performed by subjects will consist of arm movements aimed at performing an "activity" in the virtual environment (e.g. picking up a box, scrubbing a surface, drawing simple geometric shapes, ...). The interaction between the subject and the BURT system will be set using either cooperative or competitive control strategies. Augmented feedback modalities (i.e. the application of gains to "magnify" aspects of the display of error-related information) will be tested. Also, the selected set of games will allow us to test different feedback modalities (e.g. visual and auditory cues) and different control modalities. Task challenge for each training device will be incrementally increased or decreased based on participant performance.

All participants will receive 1 hour sessions, 2-3x/week for 6 weeks (total 18 sessions). Sessions will be organized with 30 minutes of robotic-assisted training and 30 minutes of hands-on training with a research therapist to work on the baseline goals of the subject. Hands-on training will be done with routinely employed techniques in therapy to transfer the skills gained with the robotic device in everyday life activities.

Participants may miss up to 3 appointments, and we will reschedule the following day or week at a time that is mutually convenient. Participants who miss 4 consecutive appointments may be removed from the study.

• Visit number 21:

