End-of-intervention outcomes assessment battery. We will repeat the same battery as performed in study visit number 2. Additionally, we will gather qualitative feedback under the form of a questionnaire in regard to the usability and the design characteristics of the device (the same questionnaire will be to study volunteers and study staff with clinical expertise (e.g. therapists and physiatrists)). The content of the questionnaires will be focused on aspects of the BURT system design such as the following: the ease of setting up the system; the comfort level achieved by the design of the human-robot interface; the effectiveness of the visual display of error feedback; the intuitiveness of the haptic feedback; the types of therapeutic exercises enabled by the system; the clarity of the instructions provided to guide the performance of

exercises. Feedback will be gathered using a visual analogue scale. We will also take note of any other comments study participants and study staff with clinical expertise might have. Study staff will guide the subject thru the questionnaire and be readily available to answer any question.

Assessments: Baseline

18 sessions:
Robotic-assisted upper extremity training

Assessments: End-of intervention

Schema 1: study procedures flow

For studies involving treatment or diagnosis, provide information about standard of care at Partners (e.g., BWH, MGH) and indicate how the study procedures differ from standard care. Provide information on available alternative treatments, procedures, or methods of diagnosis.

Standard of care for individuals with chronic motor impairments >6 months' post stroke does not typically involve upper extremity rehabilitation. However, individuals with stroke may at times be involved in standard occupational therapy intervention to address upper extremity motor impairments and optimize functioning during basic activities of daily living (ADL) and instrumental ADLs (e.g. cooking, shopping etc.). The study interventions differ from standard care in that robot training activities provide a much higher number of movement repetitions than is possible during conventional rehabilitation practice.

Describe how risks to subjects are minimized, for example, by using procedures which are consistent with sound research design and which do not unnecessarily expose subjects to risk or by using procedures already being performed on the subject for diagnostic or treatment purposes.

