The criteria for continued participation and participant removal from the study are as follows: we will allow participants to miss up to 3 appointments and will reschedule the following day or week at a time that is mutually convenient. We will remove participants from the study after 4 consecutive missed appointments.

In case in which a subject experiences discomfort they will be free to remove the system and end their participation in the study.

Videos of the sessions will be locked in cabinets and on password protected encrypted computers.

FORESEEABLE RISKS AND DISCOMFORTS

Provide a brief description of any foreseeable risks and discomforts to subjects. Include those related to drugs/devices/procedures being studied and/or administered/performed solely for research purposes. In addition, include psychosocial risks, and risks related to privacy and confidentiality. When applicable, describe risks to a developing fetus or nursing infant.

• The BURT is equipped with actuated components (i.e. motors) capable of independent motion. Risks are minimal when the BURT is used according to instructions. Small injuries, such as bruising or stretching can occur in rare cases, however, numerous safety features and procedures have been implemented to minimize risk of injury. These include a system controller designed to avoid excessively fast movements of the upper extremity joints; safety limits set for the estimated interaction forces during arm motions, and two emergency switches to immediately shut off robot power in the event of a malfunction. Height adjustments of the BURT will be performed with caution so injury does not occur when

lowering the device to ensure proper positioning for therapy. The straps of the device may cause redness of the skin. We will assure proper upper limb positioning during intervention and will pad the straps as needed so they are comfortable for the subject. Performing the tasks may cause muscle soreness similar to the potential soreness from normal daily activities.

 Being videotaped poses a privacy risk. These videos could be seen by people outside of the study staff who may be able to recognize your face. We will lock these videos in cabinets and on password protected encrypted computers that only study staff associated with the study can access.

EXPECTED BENEFITS

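### After 4 consecutive missed appointments the protocol says both that removal from the study may follow and that it will; with no exit assessment described, a removed participant's end-of-intervention outcomes would naturally be lost

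*Protocol*

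**What the plan says.** The protocol treats missed appointments twice, both times under Research Design and Methods.

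- **Visit number 3-20:** up to 3 missed appointments are rescheduled, and then "Participants who miss 4 consecutive appointments may be removed from the study".
- **Methods for ensuring subject safety, just before Foreseeable Risks and Discomforts:** the paragraph opens with "The criteria for continued participation and participant removal from the study are as follows", repeats the allowance of 3, and ends with "We will remove participants from the study after 4 consecutive missed appointments".

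The outcome schedule has two points. Visit number 2 is the baseline battery, where the ranking is given: "The Fugl-Meyer is our primary outcome measure and the Goal Attainment Scale our secondary outcome measure". Visit number 21 closes the study: "We will repeat the same battery as performed in study visit number 2". The structured feedback is placed at that same visit, where "we will gather qualitative feedback under the form of a questionnaire in regard to the usability" and the design of the device.

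On timing, all visits fall within 7 weeks: "The total duration may vary within this 7 week period to accommodate missed study visits". Training is 18 sessions over 6 weeks. Enrolment is up to 10 stroke survivors.

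**The concern.** One trigger has two consequences. Staff following the visit description could keep a participant whom the safety text obliges them to remove. The form prompt above the safety text asks for objective removal criteria, and a discretionary version elsewhere weakens the answer.

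The more practical matter is what removal carries with it. Both sentences take the participant out of the study, not just out of training. Visit 21 is the only occasion after baseline when the Fugl-Meyer, the Goal Attainment Scale and the questionnaire are collected, and the protocol describes no route to that visit for someone already removed. If such participants are not assessed, the before-after results and the structured usability ratings come only from people who kept up the schedule. The primary aim asks whether the device suits long-term interventions, so those who could not keep up are informative. A statistical analysis plan cannot recover measurements that were never taken.

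**Working it through.** The protocol states no power calculation, test or dropout rate that bears on this point, so there is no figure of its own to reproduce. The check is a comparison of texts plus simple counts.

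**1. The two rules side by side**

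| | Visit number 3-20 | Safety text, removal criteria |
|---|---|---|
| Misses allowed and rescheduled | up to 3 | up to 3 |
| Trigger | 4 consecutive misses | 4 consecutive misses |
| Force | discretionary (*may*) | mandatory (*will*) |
| Removed from | the study | the study |

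The rows differ only in force. Both texts are current.

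**2. Is there any assessment after removal?** Outcome assessments appear at Visit 2 and Visit 21 only. The remuneration text under Recruitment Procedures agrees: it pays for up to 2 assessment sessions. No exit or early-termination visit appears in the visit descriptions, the removal criteria or the consent text on stopping participation.

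**3. Size of one loss.** With n participants, one missing Visit 21 takes 1/n of the participant data from that visit. At the maximum, n = 10, this is 1/10 = 10%. With fewer enrolled it is larger.

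**4. How much training could a removed participant have had?** Missed appointments are rebooked, and a rebooked appointment can also be missed. A participant who has completed 17 sessions, misses the 18th and then misses three rebookings of it has missed 1 + 3 = 4 consecutive appointments. Sessions completed: 17/18 = 94%. At the other end, a participant who misses the first 4 appointments has completed 0/18 and cannot rate the device.

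**5. Does the timetable force training to stop?**

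- Pace implied: 18 sessions / 6 weeks = 3 per week.
- Absence of 4 appointments at that pace: 4/3 = 1.33 weeks.
- Time left in the 7-week window: 7 - 1.33 = 5.67 weeks.
- Pace then needed for 18 sessions: 18/5.67 = about 3.2 per week, before Visits 1, 2 and 21 are placed.

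That is only slightly above 3 per week, and next-day rescheduling is allowed.

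**6. Cost of one Visit 21.** Planned remuneration is 2 × $50 + 18 × $5 = $190, which matches the stated maximum. The $50 for the second assessment is therefore already in the budget.

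**The case against.** The strongest reply is that this is a mismatch of one word. Trigger and allowance agree, the safety text presents itself as the criteria and so naturally governs, and changing one word under Visit number 3-20 would settle it. That is a fair account of the contradiction, but it leaves the mandatory rule in force with no exit assessment.

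The second reply is that the study is about usability. It is single-arm with no stated hypothesis test, and much of its evidence comes from the sessions, the sensors and the clinicians. Removal does not erase any of that, and a removal is itself a feasibility result. There is also a separate usability conversation with no stated timing: "The stroke survivors will participate in a question and answer formatted discussion with research staff to discuss the usability of the device". It may take place before removal. All of this stands and keeps the severity low. It does not bring the loss to zero, because the Fugl-Meyer is the named primary outcome measure and the structured questionnaire is tied to Visit 21.

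Three stronger readings are tempting, and the document does not support them:

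- *The protocol states that removed participants go unassessed.* It does not say so, nor does it forbid assessing them. The loss follows from removal from the study together with the absence of any exit visit.
- *A removed participant can have completed at most 14 of 18 sessions.* This treats the 4 misses as 4 different sessions. Because rebookings can also be missed, the count can reach 17.
- *The 7-week limit means training must end after 4 misses.* A pace of about 3.2 per week would still fit 18 sessions, so the timetable does not settle whether training should stop.

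Nor do the documents show in which direction the reported change or ratings would shift.

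**Conclusion.** The inconsistency is real. Followed as written, the mandatory rule would naturally cost a removed participant's Visit 21 Fugl-Meyer, Goal Attainment Scale and questionnaire. Each such loss is up to one before-after pair of at most 10. The figure is an upper bound on what the rule itself causes, because some of these participants would not have come to Visit 21 anyway. The loss would be selective, since it falls on poor attenders, some of whom may have had nearly the full course of training.

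The conclusion rests on one inference: that removal from the study, with no exit visit described, means no end-of-intervention assessment. How often this would happen is unknown, because the protocol gives no miss rate. The severity is minor, and the change is worth making because it is cheap.

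**What to change.** 1. Use the same wording under Visit number 3-20 and in the removal criteria on whether training stops after 4 consecutive missed appointments. Either a mandatory stop or the investigator's discretion would do; discretion leaves room for someone to return after a short absence.
2. State that stopping training does not end study participation.
3. Invite every participant who had at least one BURT session and has not withdrawn consent to the Visit 21 battery and questionnaire within the 7-week period.
4. Report the number of sessions attended by each participant, so that outcomes and ratings can be read against exposure.

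The cost is a wording change in two places and, for each such participant who agrees, one visit that is already planned and budgeted: $50 and about 1.5 to 2 hours, plus the questionnaire. Some will decline, and a stop late in the 7 weeks leaves little time to book the visit, so the loss is reduced but not removed.
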